4.3 Lifestyle Considerations

Substance abuse is not permitted during the study and subjects with a history of substance abuse 1 year prior to Visit 1 will be excluded from the study.

Subjects are required to refrain from wearing contact lenses for the duration of the study. Subjects not willing or able to refrain from wearing contact lenses will be excluded from the study.

Subjects should not have any planned ocular surgeries while participating in the study (Visit 1 – Visit 6). Investigators should discuss with the Medical Monitor should an ocular surgery become necessary while a subject is participating in the study.

4.4 Screen Failures

Screen failures are defined as subjects who consent to participate in the clinical study but are not subsequently randomly assigned to the study intervention or entered in the study. A minimal set of screen failure information is required to ensure transparent reporting of screen failure subjects, to meet the Consolidated Standards of Reporting Trials (CONSORT) publishing requirements and to respond to queries from regulatory authorities. Minimal information includes demography, screen failure details, eligibility criteria, and any serious adverse event.

Individuals who do not meet the criteria for participation in this trial (screen failure) because of the following may be rescreened.:

- Prohibited medications from which the subject may discontinue for the purposes of eligibility and / or participating in the study (with approval from the Investigator based on clinical safety).
- Exclusionary medical history status at the time of screening that will change (e.g., ocular infection, surgical history duration).

Rescreened subjects should be assigned a new subject number.

4.5 Strategies for Recruitment and Retention

It is anticipated that approximately 90 subjects will need to be screened to achieve 60 qualified completed subjects (20 per arm) for the study. Subjects will be mostly recruited from the patient population at participating study centers in the US. Subject retention is not considered a major issue for this study due to the relatively short duration.

5 Study Treatment(s) or Intervention(s)

5.1 Investigational Product(s)

Three (3) investigational products (IPs) will be administered during this study:

- VVN539 ophthalmic solution 0.02% (3mL in 5 mL bottles)
- VVN539 ophthalmic solution 0.04% (3mL in 5 mL bottles)
- VVN539 ophthalmic solution vehicle (3mL in 5 mL bottles)

5.1.1 Description

VVN539 ophthalmic solution will be supplied to study sites in 5mL low-density polyethylene LPDE multidose droppers filled with at least 3 mL solution. Table 1 describes the composition and general information about VVN539 supplied for this study. The VVN539 vehicle control has the same composition as VVN539 ophthalmic solution except that it does not contain VVN539. Additional detail can be found in the Investigator's Brochure.

Table 1: VVN539 Ophthalmic Solution General Information

Dosage Form	Sterile solution
Active Ingredient	0.02% or 0.04% VVN539
Inactive Ingredients	Benzalkonium chloride, Polyvinylpyrrolidone (PVP) K90, Poloxamer 407, glycerin, boric acid, sodium borate, water
Route of Administration	Topical ocular administration
Physical Description	Isosmotic, clear solution
pH	Approximately 5.0
Pharmacokinetics	VVN539 metabolite and nitric oxide active moieties dosed q.d. or b.i.d
Stability	12 months expiry for samples stored at 5°C temperature

5.1.2 Dosage and Administration

Eligible subjects will be randomized in a 1:1:1 ratio to receive either 0.02% or 0.04% VVN539 or vehicle control. The IP will be administered as 1 drop either q.d. or b.i.d in the inferior conjunctival fornix in each eye.

The first dose of VVN539 will be administered in clinic after the 8:00AM IOP has been measured at Visit 3. The subjects will then receive the bottle of IP and will self-administer the IP in the morning (suggested timing between 7:00AM and 9:00AM) each day for 5 days. The study site should call the subject the day prior to Visit 4 to remind them to NOT dose in the morning at home on the day of the visit. The last day of q.d. morning dosing will be Visit 4 when subjects will be dosing in clinic after the 8:00AM IOP has been measured.

Starting the day after Visit 4, subjects will self-administer the IP in the evening (suggested timing between 7:00PM and 9:00PM) each day for 6 days. The last q.d. evening dose will be administered in the evening Visit 5 after the last IOP has been measured.

Starting the day after Visit 5, subjects will self-administer the IP b.i.d (suggested timing between 7:00AM and 9:00AM for the morning dose and between 7:00PM and 9:00PM for the evening dose) each day for 6 days. The study site should call the subject the day prior to Visit 6 to remind them to NOT dose in the morning at home on the day of the visit. The last morning dose will be administered in clinic after the 8:00AM IOP dose has been measured. Subjects will return the IP at Visit 6 and will resume their standard of care treatment.

Subjects should be instructed to administer missed doses as soon as possible, as long as it is not administered within 12 hours of the next scheduled dosing during the q.d. dosing periods or not within 4 hours of the next scheduled dosing during the b.i.d dosing period. Missed doses will be recorded as deviations in the electronic case report form (eCRF).

5.2 Preparation/Storage/Handling/Accountability

5.2.1 Acquisition and Accountability

VVN539 ophthalmic solution and vehicle will be provided to study sites in identical bottles so that masking is maintained. Shipment records will be verified by comparing the shipment inventory sheet to the actual quantity received at the site. Accurate records of receipt and disposition of the IP (e.g. dates, quantity, subject number, date dispensed, date returned) must be maintained by the study site. At the end of the study, all used and unused IP will be returned to VivaVision (or designee), following approval by VivaVision. The study monitor (or designee) will verify IP accountability prior to return of the IP. All accountability procedures must be completed before the study is complete or before the study site is closed, whichever comes first.

5.2.2 Product Packaging and Labeling

Each randomization kit contains one dropper bottle of IP sufficient for 14-18 days of q.d. and 7-9 days of b.i.d. dosing. Double masked labels will minimally contain the following information:

- Protocol number
- Sponsor's name
- Kit number
- Instructions for use
- Storage temperature
- Required statement(s) per regulatory agency

5.2.3 Product Storage and Stability

IP and active comparator should be stored at controlled refrigerated temperatures from 2°C to 8°C and protected from light. Once dispensed to the subject, IP bottles may be stored by the subject in the refrigerator (approximately 2-8°C/35-46°F) or at ambient room temperature until use.

5.3 Measures to Minimize Bias: Randomization and Blinding

Subjects will be randomized to a treatment assignment. A randomization schedule will be generated by qualified personnel independent of the project team and study conduct and maintained in a secure and limited-access location separate from the Investigators and members of the project team. Treatment will not be blocked by study site which essentially stratifies the treatment by study site. Treatment assignments will be masked to the Sponsor, subjects, Investigators, and investigative staff, until completion of the study and the final database is locked. Appropriate precautions will be taken to prevent unauthorized access to the randomization scheme.

Both doses of VVN ophthalmic solution as well as vehicle will be provided in identical dropper bottles to prevent inadvertent unmasking. If unmasking is required, the integrity of the study assessments and objectives will be maintained by limiting access to the unmasked data. Unless the subject's safety requires otherwise and if time permits, the decision to unmask an individual subject's treatment assignment is to be made jointly by the Investigator and medical monitor after consultation with the Sponsor, thus leaving the masking of the remaining subjects intact.

5.4 Treatment Adherence

Adherence to the treatment schedule will be assessed by site staff by querying subjects at Visits 4-6 whether they missed any doses in the dosing period preceding the visit and if so, whether 2 or more doses were missed. Subjects should be counseled on the importance of adhering to the dosing scheduled. Missed doses will be recorded as deviations in the eCRF.

5.5 Concomitant Therapy

All medications that the subject has taken 2 months prior to Visit 1 and / or is taking through Visit 6 (or discontinuation from the study) will be recorded in the subject chart and the eCRF. The generic name of the drug, dose, route of administration, duration of treatment (including start and stop dates), frequency, indication and whether or not the medication was taken due to an AE will be recorded for each medication.

For this protocol, a prescription medication is defined as a medication that can be prescribed only by a properly authorized/licensed clinician. Medications to be reported in the case report form are concomitant prescription medications, over-the-counter medications and supplements.

The medications and therapies listed in Table 2 are exclusionary for the study and / or are prohibited during study participation. Investigators should discuss with the Medical Monitor should any of these medications or procedures become medically necessary for a subject during study participation.

Table 2: Medications and Procedures Not Permitted

Medication / Procedure	Eye	Limitation
Intraocular implant for IOP treatment, glaucoma filtering surgery, placement, or removal of minimally invasive glaucoma implant (MIGS)	Study Eye	Exclusionary any time prior to Visit 1
Laser IOP lowering surgery in the study eye	Study Eye	Exclusionary if performed within 6 months of Visit 1
Laser peripheral iridotomy for narrow angle in study eye	Study Eye	Exclusionary if performed within 3 months of Visit 1
Ocular trauma in the study eye	Study Eye	Exclusionary if occurred within 6 months of Visit 1
Surgery involving the ocular surface (including cataract surgery) or non-IOP-lowering laser in the study eye	Study Eye	Exclusionary if performed within 3 months of Visit 1
Refractive surgery (including but not limited to radial keratotomy, PRK, LASIK)	Study Eye	Exclusionary any time prior to Visit 1 and prohibited during study participation
Intravitreal corticosteroid injection	Either Eye	Exclusionary if performed within 6 months of Visit 1
Subtenon/subconjunctival steroid injection	Either Eye	Exclusionary if performed within 3 months of Visit 1
Ocular infection, inflammation, clinically significant blepharitis, conjunctivitis, or of herpes simplex keratitis	Either Eye	Exclusionary if occurred within 2 months of Visit 1
Contact lens use	Either Eye	Prohibited during study participation
Ocular medication of any kind other than: 
• Ocular hypotensive medications which must be washed out according to the provided schedule• Ocular Medication as part of an eye exam• Lubricating drops for dry eye	Either Eye	Exclusionary within 28 days of Visit 1 and prohibited during study participation
Ocular hypotensive medication	Either Eye	Subjects on ocular hypotensive medication must wash out prior to Visit 2 See section 5.5.1 for use of ocular hypotensive medication other than IP during study participation
Changes of systemic beta blockers that in the opinion of the investigator could have a substantial effect on IOP	N/A	Exclusionary within 30 days of Visit 1 and prohibited during study participation
Systemic corticosteroids (oral, injectable, inhaled) within 30 days of Visit 1 or planned use during the study. 
• Topical dermatologic steroids are allowed if used for less than 3 consecutive days on no more than 3 separate areas of the body and the dosage is not expected to increase during the study.• Intranasal steroids are allowed if used less than or 4 times per week and the dosage is not expected to increase during the study.	N/A	Exclusionary within 30 days of Visit 1 and prohibited during study participation

Medication / Procedure	Eye	Limitation
Substance abuse	N/A	Exclusionary within one year of Visit 1 and prohibited during study participation

5.5.1 Management of Elevated IOP During Treatment

Any subject who has an elevated IOP that the PI considers unsafe for the subject may be rescued and placed on appropriate alternate therapy. The choice of rescue medication is at the Investigator's discretion. Rescue medication should be entered into the eCRF with annotation indicating that the medication was used for rescue.

Rescued subjects will be considered as treatment failures, and the need for rescue therapy will not be considered an adverse event (AE). Rescued subjects will stop the investigational product and should not be withdrawn from the study.

The following guidance is provided to Investigators for rescue and the decision to rescue is at the discretion of the investigator's judgement:

- Ocular hypotensive medication (other than IP) is prohibited during study participation unless the subject is rescued.
- If the subject's IOP is > 36 mm HG, the Investigator may recheck the IOP within 3 day of the visit and rescue medication may be considered if the IOP remains elevated
- Rescued subjects should discontinue the investigational product.
- Rescued subjects should continue in the study for safety follow-up after receiving the rescue medication.

6 Study Discontinuation/Subject Withdrawal

6.1 Discontinuation of Study Treatment or Intervention

IP may be discontinued by a subject at any time. In addition, the Investigator or Sponsor can discontinue a subject from further IP administration for other reasons related to the best interest of the subject.

6.2 Subjects Discontinuation/Withdrawal from the Study

Subjects are free to withdraw from participation in the study at any time upon request. An Investigator may discontinue or withdraw a subject from the study for the following reasons:

- IOP measurement of 36 mmHg or higher in either eye
- Severe ocular irritation, burning, pain, or hyperemia
- Study terminated by the Sponsor, Food and Drug Administration (FDA), or other regulatory authorities
- Any woman who becomes pregnant while participating in the study. Information on the pregnancy and outcome will be requested.
- Significant study treatment/intervention non-compliance
- If any clinical adverse event, laboratory abnormality, or other medical condition or situation occurs such that continued participation in the study would not be in the best interest of the subject
- Disease progression which requires discontinuation of the study intervention
- If the subject meets an exclusion criterion (either newly developed or not previously recognized) that precludes further study participation

The reason for subject discontinuation or withdrawal from the study will be recorded on the case report form. Subjects who sign the informed consent form and are randomized but do not receive the study intervention may be replaced. Those who sign the informed consent form, and are randomized and receive the study treatment, and subsequently withdraw, or are withdrawn or discontinued from the study, will not be replaced.

Additionally, the trial or parts of the trial may be discontinued by the Sponsor or at the recommendation of the Investigator after consultation with VivaVision Biotech, Inc. This may be based on a significant number of AEs of a similar nature that warrant such action.

In the event study discontinuation of a randomized subject is necessary, the Investigator should make every attempt to have the subject complete all Visit 6 assessments. If a non-serious AE is unresolved at the time of the subject's final study visit, an effort will be made to follow up until

the AE is resolved or stabilized, the subject is lost to follow-up, or there is some other resolution of the event. The Investigator should make every attempt to follow all SAEs to resolution.

6.3 Lost to Follow up

A subject will be considered lost to follow-up if he or she fails to return for scheduled visits and is unable to be contacted by the study site staff.

The following actions must be taken if a subject fails to return to the clinic for a required study visit:

- The site will attempt to contact the subject and reschedule the missed visit within 1-2 days and counsel the subject on the importance of maintaining the assigned visit schedule and ascertain if the subject wishes to and/or should continue in the study. Subjects should continue the current dosing regimen until the rescheduled visit.
- Before a subject is deemed lost to follow-up, the Investigator or designee will make every effort to regain contact with the subject (where possible, 3 telephone calls and, if necessary, a certified letter to the subject's last known mailing address or local equivalent methods). These contact attempts should be documented in the subject's medical record or study file.
- Should the subject continue to be unreachable, he or she will be considered to have withdrawn from the study with a primary reason of lost to follow-up.

7 Study Procedures

Written informed consent and Health Insurance Portability and Accountability Act (HIPAA) authorization will be obtained from all subjects prior to any study-related procedures being performed. The Schedule of Procedures and Assessments ([Appendix 1](#)) lists the procedures that should occur at each study visit. Details for the study assessments can be found in Appendices 3-12.

7.1 Visit Descriptions

7.1.1 Screening (Visit 1, Day -35 to -1)

The following procedures will be performed on all subjects at the screening visit. Ophthalmic procedures should be performed in the order suggested below:

- Explain the purpose and conduct of the study to the subject, answer the subject's questions, and obtain written informed consent and HIPAA authorization.
- Obtain information including: demographics, concomitant medications, ocular and systemic medical and medication history and surgical history.
- Determine study eligibility based on Inclusion/Exclusion criteria.
- Best corrected visual acuity (BCVA)
- Perimetry
 - Visual field within 3 months of Visit 1 is acceptable, provided that it is reliable meets the requirement for automated threshold visual field (e.g., 30-2 or 24-2 Humphrey). Unreliable entry fields must be repeated prior to study drug dispensation.
- OCT
 - OCT within 3 months of Visit 1 is acceptable.
- Slit-Lamp Biomicroscopy
- IOP measurement
 - Measured using Goldmann applanation tonometer and a two-person reading method.
 - Measure twice in each eye; if results differ by >1 mm Hg, a third measurement will be taken. The mean will be taken if two measurements are used, for 3 measurements record the median.
- Pachymetry
- Gonioscopy
 - Gonioscopy performed within 3 months of Visit 1 is acceptable
- Dilated ophthalmoscopy

- Determine cup-disc ratio
- Blood pressure & heart rate
- Blood chemistry, hematology
- Urine pregnancy test (UPT) for women of childbearing potential
 - An adult woman is considered to be of childbearing potential unless she is one year post-menopausal or three months post-surgical sterilization.
- Instruct subjects who were on ocular hypotensive medication prior to the visit to start washout based on the table below. Subjects may be changed to a another IOP lowering therapy with a shorter washout period as long as the appropriate washout is met prior to Visit 2.

Ocular Hypotensive Medication Class	Minimum washout period
Prostaglandins	
β-adrenoceptor antagonists	4 weeks
Kinase inhibitors	
Adrenergic agonists	2 weeks
Muscarinic agonists	
Carbonic anhydrase inhibitors	5 days

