3.1 Overall Design of the Study

This is a prospective, parallel-comparison, multi-center, double-masked, randomized, vehicle-controlled dose-response study assessing the safety and ocular hypotensive efficacy of VVN539 in subjects with POAG or OHT. Approximately 60 subjects will be randomized into one of two active treatment arms or a control arm (20 subjects per cohort):

- Arm 1: 0.02% VVN539 ophthalmic solution
- Arm 2: 0.04% VVN539 ophthalmic solution
- Arm 3: VVN539 ophthalmic solution vehicle

Treatment assignments will be masked to VivaVision, study subjects, Investigators, and site staff.

The study involves 6 clinic visits, including screening, baseline, and treatment visits. The study is open to subjects with OHT and POAG who are either treatment-naïve or are already on ocular hypotensive medication. Subjects on ocular hypotensive who meet screening inclusion and do not meet screening exclusion criteria at Visit 1 will discontinue their prior ocular hypotensive medication for up to 35 days before returning to the site for Visit 2 (baseline). Treatment naïve subjects can return for the baseline visit as early as the day after Visit 1. Subjects meeting all baseline inclusion criteria and none of the baseline exclusion criteria will be randomized into one of the study arms and will return to the study site the next day for the first treatment. Three different dosing regimens (once a day [q.d.] in the morning, q.d. in the evening and twice a day [b.i.d.]) will be tested for 7-9 days, each.

Figure 1: Study Treatment

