 - Shaffer grade < 3 (in 1 or more quadrants)
 - Gonioscopy within 3 months prior to Visit 1 is acceptable.
15. Cup-disc ratio of 0.7 or greater in either eye.
16. Nerve fiber layer thickness assessment by Optical Coherence Tomography (OCT) documents thinning of the NFL into the abnormal range for either eye.
 - If, in the opinion of the investigator, the thinning of the NFL may be attributed to other ocular features (including but not limited to optic nerve drusen, myopia, chorioretinal scars), then the subject is allowed.
17. Subjects with visual fields with substantial glaucomatous loss (e.g., Bjerrum scotoma, blind spot enlargement) for whom washout and potential randomization would be unsafe.

18. In addition to the above criteria, glaucomatous damage in either eye so severe that washout of ocular hypotensive medications for up to 5 weeks and treatment for 3 weeks (for subjects randomized to vehicle control) is not judged safe in the opinion of the Investigator.
 - Note: Subjects may be changed to a another IOP lowering therapy with a shorter washout period as long as the appropriate washout is met prior to Visit 2.
19. Any abnormality preventing reliable applanation tonometry of either eye.

General/Systemic:

20. Laboratory tests indicative of any clinically significant disease in the opinion of the Investigator.
21. Clinically significant systemic disease (e.g., uncontrolled diabetes, myasthenia gravis, hepatic, renal, cardiovascular or endocrine disorders) which might interfere with the study in the opinion of the Investigator.
22. Participation in any study involving an investigational product (IP) within the past 30 days of Visit 1.
23. Changes of systemic beta blockers during the study that in the opinion of the Investigator could have a substantial effect on IOP within 30 days prior to Visit 1 or anticipated during the study.
24. Have received systemic corticosteroids (oral, injectable, inhaled) within 30 days of Visit 1 or planned use during the study.
 - Note: Topical dermatologic steroids are allowed if used for less than 3 consecutive days on no more than 3 separate areas of the body within 30 days of Visit 1 and the dosage is not expected to increase during the study.
 - Intranasal steroids are allowed if used less than or 4 times per week within 30 days of Visit 1 and the dosage is not expected to increase during the study.
25. History of substance abuse within 1 year of Visit 1

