7.1.2 Randomization (Visit 2, Day 0)

The following procedures will be performed on Day 0 (randomization). Ophthalmic procedures should be performed in the order suggested below:

- Determine study eligibility based on Inclusion/Exclusion criteria.
- BCVA
- Biomicroscopy
- Diurnal IOP
 - Measured using Goldmann applanation tonometer and a two-person reading method.
 - Readings at:
 - 8:00AM (± 30 mins)
 - 10:00AM (± 30 mins)
 - 4:00PM (± 30 mins)
 - Measure twice in each eye; if results differ by >1 mm Hg, a third measurement will be obtained. The mean will be taken if two measurements are used, for 3 measurements record the median.
- Blood pressure & heart rate
- Randomization
- Urine pregnancy test (UPT) for women of childbearing potential

- An adult woman is considered to be of childbearing potential unless she is one year post-menopausal or three months post-surgical sterilization.
- Assess subject ability to instill drops in eye using artificial tears. Subjects should be retrained on the correct way to instill drops if they are not able to do so.
- Update medical and ocular history, as needed
- Update concomitant medications, as needed

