9.8. CHANGES IN THE CONDUCT OF THE STUDY OR PLANNED ANALYSES

9.8.1. Protocol Amendments

Amendment 1 of protocol made the following notable changes:

- Revised exclusion criteria to minimize the risk of study subjects randomized to vehicle for potential glaucomatous loss;
- Allowed investigators to switch subjects who were previously treated with an ocular hypotensive medication with a 4 week washout period to a ocular hypotensive medication with a shorter washout period provided the appropriate washout is met prior to Visit 2.

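### An unreliable entry visual field need only be repeated by drug dispensation, which falls after washout and one day after randomization, the two steps whose safety exclusion 17 uses the field to judge

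*Protocol*

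**What the plan says.** Perimetry is a Visit 1 procedure (Protocol 7.1.1). A field from the 3 months before Visit 1 is accepted if it is reliable, and Appendix 9 defines reliable as fixation losses, false positives and false negatives each of at most 33%. If the entry field fails, the rule is "Unreliable entry fields must be repeated prior to study drug dispensation". It stands in Section 7.1.1, in footnote 9 of Protocol Appendix 1 and in footnote 9 of SAP Appendix I.

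Exclusion 17 (Protocol 4.2) turns on the field. It excludes subjects with substantial glaucomatous field loss "for whom washout and potential randomization would be unsafe".

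On sequence, Section 7.1.1 tells the site at Visit 1: "Instruct subjects who were on ocular hypotensive medication prior to the visit to start washout based on the table below". Section 3.1 reserves that step for "Subjects on ocular hypotensive who meet screening inclusion and do not meet screening exclusion criteria at Visit 1". At Visit 2 (Day 0) the site must "Determine study eligibility based on Inclusion/Exclusion criteria" and then randomize. Section 3.1 says that eligible subjects "will be randomized into one of the study arms and will return to the study site the next day for the first treatment". Section 7.1.3 places the first dose and the first dispensing at Visit 3 (Day 1).

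A note to exclusion 18, repeated in 7.1.1, allows bridging: "Subjects may be changed to a another IOP lowering therapy with a shorter washout period".

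**The concern.** The field informs two decisions: whether a treated subject can safely stop medication, and whether any subject can safely be randomized, with a one-in-three chance of vehicle. The only date given for putting an unreliable field right comes after both. A site that starts washout on an unreliable field and repeats it on the morning of Day 1 has met the specific rule, yet exclusion 17 had to be judged without a usable test.

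At stake is the safety of a subject whose field loss the other entry criteria miss. According to Protocol Appendix 16 and SAP 9.8.1, Amendment 1 was made to reduce the risk of glaucomatous loss in subjects randomized to vehicle. A repeat deadline after randomization fits poorly with that aim.

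**Working it through.** The plan gives no figure on this point, so there is none to reproduce. The check is of visit order and of what the other provisions require.

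**Inputs**
- Screening window: Day -35 to Day -1 (7.1.1).
- Washout: instructed at Visit 1, to be complete before Visit 2 (7.1.1; Table 2).
- Minimum washout: 4 weeks for prostaglandins, beta-blockers and kinase inhibitors; 2 weeks for adrenergic agonists; 5 days for muscarinic agonists and carbonic anhydrase inhibitors (Appendix 1, footnote 1).
- Randomization: Day 0 (7.1.2). First dispensation: Day 1 (7.1.3).

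**Step 1. Deadline against randomization.** Day 1 − Day 0 = 1 day. A repeat that meets the rule can come after randomization.

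**Step 2. Deadline against washout.** Washout ends by Day 0, so the deadline lies beyond the whole of it. Minimum time off the prior drug by Day 1:
- 4-week classes: 28 + 1 = 29 days
- 2-week class: 14 + 1 = 15 days
- 5-day classes: 5 + 1 = 6 days

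If the drug was stopped on Day -35, the time is 35 + 1 = 36 days. Time off the prior drug is not always untreated time. A user of a 4-week class who is bridged has a minimum untreated time of 5 + 1 = 6 days (5-day class) or 14 + 1 = 15 days (adrenergic agonist). Treatment-naive subjects have no washout, so only Step 1 applies to them.

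**Step 3. Does any other provision set an earlier date?**
- Section 3.1 and the eligibility steps at Visits 1 and 2 require that exclusions are not met. An unreliable field does not show that exclusion 17 is met; it leaves the question open.
- Appendix 9 requires reliability but gives no date for a repeat.
- The Appendix 1 schedule lists the field at Visit 1 only. Section 7.1.7 provides for unscheduled visits, including ophthalmic assessments, so a repeat can be done earlier, but nothing requires it.
- Appendix 11 shows the contrast. A laboratory sample without a result must be collected again and reviewed before Visit 2. Fields have no matching rule.

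**Step 4. What follows a failed repeat on Day 1?** Under Section 6.2 the subject can be withdrawn for an exclusion not recognized before, and replaced if undosed. Under Section 9.3 the subject remains in the Full Analysis Set, which comprises everyone randomized. For a treated subject, the washout has already taken place and cannot be undone.

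**The case against.** The strongest reply is that the rule is only a latest-by limit. Perimetry is done at Visit 1, where the washout instruction comes last in the list. Section 3.1 allows washout and randomization only when no exclusion is met, eligibility is checked again at Visit 2, and no bottle is handed over before the repeat is due. A site can satisfy all of these together, and a careful one would repeat the field at once. The laboratory rule also lets washout begin before every eligibility result has been reviewed.

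Much of this stands. The text permits a late repeat and does not direct one, and the laboratory parallel supports a deadline before randomization only. The case for a deadline before washout rests on exclusion 17, which names washout, and on Section 3.1. What the reply does not supply is a date: the general checks do not say what to do while the field is unreadable, and the one rule that does gives a date after both decisions.

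Four stronger readings are tempting, and the documents do not support them.
- A reader might infer that subjects may be randomized to vehicle with known unsafe field loss. The eligibility checks forbid that; the gap concerns loss not yet established.
- A reader might take the 29 or 36 days as harm caused by the rule. They are ordinary washout lengths plus one day, which eligible subjects undergo too.
- A reader might infer that the repeat has nowhere to take place. Unscheduled visits can host it.
- Because 7.1.3 lists the in-clinic dose ahead of dispensing, a reader might infer that the repeat may follow the first dose. Both happen at the same visit, and nothing suggests that this was intended. The point does not rely on it.

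**Conclusion.** The point holds as a minor one. The stated repeat deadline is too late for the purpose that exclusion 17 gives the field. The washout part matters most, because a treated subject can complete the whole washout before a reliable field exists. The randomization part amounts to one day and, if the repeat fails, one undosed subject left in the Full Analysis Set.

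The remaining risk is field loss not caught by cup-disc ratio (exclusion 15), nerve fiber layer thinning (exclusion 16), the Investigator's judgement of damage (exclusion 18) or safe discontinuation (inclusion 7). Bridging shortens untreated time for some subjects. The documents give no rate of unreliable fields, so the number affected is unknown. There is no material effect on the analysis.

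The conclusion assumes that dispensation means the first dispensing at Visit 3, as 7.1.3 and both schedules indicate, and that no site manual outside these documents sets an earlier date.

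**What to change.** In Protocol 7.1.1, Protocol Appendix 1 footnote 9 and SAP Appendix I footnote 9, change the deadline so that an unreliable entry field must be repeated, and a reliable one reviewed by the Investigator, before washout is started for subjects on ocular hypotensive medication, and in all cases before randomization at Visit 2. Add that an unscheduled visit may be used if the repeat cannot be done at Visit 1.

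The deadline before washout brings most of the safety benefit, since it spares an ineligible treated subject the washout altogether. The deadline before randomization matches the laboratory rule and keeps subjects who fail the repeat out of the Full Analysis Set.

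No test is added, because the repeat is already required. The cost is an occasional same-day repeat or extra visit and a slightly later start of washout. The 35-day window leaves 35 − 28 = 7 days of slack for a 4-week washout, 35 − 14 = 21 days for a 2-week washout and 35 − 5 = 30 days for a 5-day washout. Seven days is tight for the 4-week classes unless the subject is bridged. The rescreening reasons in Section 4.4 do not clearly cover an unreliable field, so a line there would help if a delayed repeat pushes Visit 2 outside the window.
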